The Radiotherapy Unit, SI Gjøvik offers EBRT to patients with cancer from Oppland and Hedmark Counties (approximately 380 000 inhabitants) and treats about 700 patients each year. About 2/3 of these are 65 years or older. Palliative treatment represents about 60% of all treatment, and is offered regardless of cancer type. Curative treatment is administered only to patients with breast-, prostate-, lung- or skin cancer. Patients with other types of cancer in need of EBRT with curative intent, or patients who need stereotactic or internal radiotherapy are referred to Oslo University Hospital

Sample size estimates: The prevalence and impact of problems uncovered by GA in older Norwegian patients receiving EBRT are not known. Neither is the frequency of the defined adverse outcomes. Thus, estimates of the sample size needed to reliably define characteristics of patients at risk for adverse outcomes cannot be made. Furthermore, our sample will be heterogeneous and several demographic, medical and GA characteristics will have to be taken into account.

Based on these considerations, we will extend the inclusion period to one year and aim at including 325 patients. This cohort, we believe, will be a representative sample, large enough to ensure that all participating municipalities are represented for the evaluation of the feasibility of GA. To achieve 325 enrolled patients within one year, we presume that 70% of the patients 65 years or older who are treated at the RTU will consent to participation.

Our hypothesis is that patients, who are classified as frail, will have increased risk of deterioration in global QoL and physical functioning (PF), assessed by the corresponding EORTC QLQ-C30 scales ranging from 0-100. A difference of 10 points on these scales is considered a clinically significant difference.⁷⁶ Based on the reported prevalence of frailty in studies of other cohorts of older patients with cancer,^{18,43} one may assume that about 40% will be frail and 60% non-frail. To detect a difference of 10 points in global QoL and PF between the two groups at 8 weeks follow up, standard deviation (SD) = 30 (a conservative estimate), power 80% and significance level 5%, 119 patients will be needed in the frail group and 178 patients in the non-frail group, in total 297 patients. To document a difference of 11 points, 247 patients are needed. Based on these estimates, and taking into account that some drop out will occur, we find that including 325 patients will be satisfactory.

Strategy for the analyses

Adverse events are defined as described under Study aims, page 7-8. The patients will be classified as frail or non-frail based on GA at baseline. Primary and secondary outcomes will be compared between the non-frail and frail using bivariate regression analyses. Since the study cohort will be heterogeneous and several factors most likely will affect the outcomes, we will also estimate multivariate regression models, adjusted for these factors. The most important factors will be type of cancer, stage of disease, gender and radiotherapy regimen. Time trend models will be estimated in order to assess the development in the primary outcomes for non-frail/frail patients during the follow up period. We will also estimate bi- and multivariate regression models to assess the impact of each individual factor in GA (i.e. comorbidity, physical function, nutritional status) on the defined outcomes. Furthermore, we will use descriptive statistics to compare sociodemographic and medical data and GA findings between patients experiencing and not experiencing adverse events.

The sensitivity and specificity of EFS in identifying frail patients will be tested against the full GA. EFS ability to predict adverse events on the defined outcomes will be assessed with uni- and multivariate regression analysis, controlled for relevant co-variates (e.g. type of cancer, stage of disease, and radiotherapy regimen).

To assess the feasibility of GA for the municipal health care service, we will partly lean on the RE-AIM Framework,⁷⁹ and evaluate the proportion of consenting and participating municipalities and explore potential difference between them. We will also evaluate the number and completeness of the GAs that are actually performed in relation to those planned. For each assessment, the municipal contact nurse, who performs the assessment, will answer a short questionnaire addressing time spent, obstacles, facilitators, patients' opinion on relevance and convenience, and actions taken due to identified problems. These data will be linked to the individual patients and thereby contribute to identify patients who may benefit the most from GA. For analyses, we will use descriptive statistics.

Analysis of muscle mass and inflammation markers: Muscle mass will be quantified by analyses of diagnostic CT scans taken within five weeks prior to start of EBRT. The analyses will be performed with special soft-ware developed for this purpose (Slice-O-Matic software V4.3 - Tomovision, Montreal, QC, Canada).^{30,51,53,80} As an indicator of inflammation, we will use the Glasgow Prognostic Score (GPS) which is based on C-reactive protein (CRP) and serum-albumin (s-alb) and is scored on a scale from 0 to 2 (0 = CRP < 10 + s-alb > 35, 1 = CRP > 10, any s-alb value, 2 = CRP > 10 + s-alb < 35).⁵⁰ The association between frailty defined by GA, GPS and muscle mass will be assessed using descriptive statistics and correlation analyses. Regression analyses will be used to assess the association with survival.

Comparison with outcomes in a subsequent pilot study: The plan is that an intervention targeting patients at risk of adverse events will be developed based on the results from the present study, and that this intervention will be tested in a pilot study before embarking on a larger randomised trial. The pilot study will have a cluster-randomized design, randomising municipalities to either control or intervention to avoid that the same staff treats both control and intervention patients. In a smaller pilot study, a cluster-randomised design may result in an imbalance in characteristics between control and intervention patients. Although this may partly be adjusted for in the analyses, it may be relevant to draw comparisons to a matched control group from the present cohort. This potential use of study data is explicitly stated in the patient information and consent form.

Data storage and protection

Data storage and management are described in detail in the Norwegian protocol with the purpose of informing the Ethical Review Board and the Data Protection Officials. In short, data storage and use will follow Norwegian laws and regulations and be approved by both the Norwegian Ethical Review Board, Health Region South-East, and the Privacy Protection Official at Innlandet Hospital Trust before study start. According to Norwegian regulations, data sharing is not possible before data are anonymised, i.e. unless the patients are specifically informed through the patient information and consent form.

Ethics

Study approval and data storage will be applied for to The Regional Committee for Medical Research Ethics, Health Region South-East (REK HSØ) and the Data Protection Official at Innlandet Hospital Trust before start of study. The study will be performed according to the rules of the Helsinki-declaration, and registered in the ClinicalTrials.gov database. Participation will not inflict upon the patients' cancer treatment and will not imply any health risks or deviation from good clinical practice. The patients will receive treatment and care according to routine practice, and all participants will provide written informed consent.

Besides the inconvenience of providing potential sensitive information and spending time to fill in questionnaires and to perform the study test, study participation inflicts little burden on the patients. The registrations are kept as simple as possible, and represent no health risks. Even so, certain ethical aspects are still relevant to discuss. Being an observational study, it is from a methodological point of view important that study participation and registrations inflict as little as possible upon the patients' routine care. However, thorough evaluations like GA will potentially uncover problems and needs that it will be ethically unacceptable not to act upon. As formerly stated, we have therefore prepared general guidelines for the project nurse and our contact nurses in the municipalities stating when actions should be considered or carried out (with patients' informed consent). These actions and the undertaken measures will be registered, both to clarify the needs for GA in older patients with cancer receiving EBRT, and also in order to interpret the results.

It is possible that the extra attention the structured assessments entails, may benefit the participating patient. Hence it might be seen as problematic that patients from non-participating municipalities do not receive the same follow up as those from municipalities agreeing to perform GA during follow-up. We find, however, no reason to believe that these GA registrations will have a significant clinical impact. Firstly, all patients will be registered and tested in the same way prior to and at completion of EBRT. Secondly, there is currently no documentation indicating that GA without management provides significant benefits for the patients. On the contrary, a recently published study⁸¹ of lung cancer patients randomized for GA or not did not report any impact of GA, except for a little less toxicity from chemotherapy. This latter finding may be explained by the fact that fewer patients in the GA group received such treatment. Thirdly, patients from non-participating municipalities will be given the opportunity to keep in touch with the project nurse or cancer nurse at the Radiotherapy Unit if they report any need for it through the questionnaire especially added for these patients. Overall, we believe that participating in this study will have the same impact on all patients.

The knowledge generated by this study will be beneficial for future patients, and we find that the possible inconvenience for the participants is exceeded by the potential benefit for the participants and for the overall group of older patients with cancer receiving EBRT.

Organization

The project is organized with a project leader, an assistant project leader, a scientific (main) and a local project group, a reference group, and user representatives. Participants and details appear in section “Project group and collaboration” below. The study will provide the basis for a doctoral thesis, completed by a PhD student, financed by the Research Department, Innlandet Hospital Trust and connected to The Research Centre for Old Age Psychiatry (AFS). AFS will also serve as the project office.

A project nurse in a full-time position, financed by the Research Department, Innlandet hospital trust will be employed before the study starts in February 2017. He/she will be a professional cancer nurse and will have the daily responsibility for the data collection. Furthermore, he/she will be a key person in the collaboration with the municipal health services, and will have a co-responsibility for training of the municipal contact nurses who will perform the follow-up GA registrations. The project nurse will continuously be available for the municipal health services for guidance, and will have all necessary access to academic expertise from local geriatricists, geriatric nurses, cancer nurses and oncologists, all represented in the scientific and the local project group. If the project nurse is intermittently absent (holidays etc.), the PhD student (a physician) will be responsible for patient inclusion, registrations and data collecting. The PhD student will receive the necessary training from the project nurse and participants in the project group.

The study conduct will depend on a good collaboration with the municipal health services in Hedmark and Oppland counties. To achieve this, the project is linked to the existing “Network of nurses for the severely ill”, as formerly explained (page 9). Four nurses from this network have collaborated with the scientific project group in the study design (including the scheduled registrations), and will continue to participate in the further study conduct. There is also established a larger reference group comprising municipal cancer contact nurses and cancer coordinators. Before the study commences, a cancer contact nurse, preferably a cancer nurse, from each participating municipality will be assigned to the project and the reference group. Additionally, participants in the reference group from general practitioners (GPs) in the area are warranted. To achieve this, the plan is to contact the local GPs union in the two counties.

Participation in the study must be anchored to the health care management in each municipality. Thus, all 46 municipalities in Hedmark and Oppland have received written information about the study, and a final confirmation or rejection of their participation will be retrieved before study start.

Future contact with the municipal health care service will be maintained through email, phone, video conferences, and established meeting points. For those nurses who will participate in GA registrations, meetings/seminars for training will be arranged. Participation will not be charged, and travel expenses will be covered.

User participation

A group of four user representatives has been established. So far, they have participated in the planning of the study, and also evaluated and approved the scheduled registrations. These representatives will continue their collaboration throughout the study conduct, and will also participate in interpreting and dissemination of results.

Project group and collaboration

The project emerges from Innlandet Hospital Trust (SI) and will be performed in collaboration with the municipalities in Hedmark and Oppland counties and several internal and external partners, including the Norwegian University of Science and Technology (NTNU) Campus Gjøvik. [name] (prof., MD, oncologist), SI will lead the project. Co-leader is [name] (prof, ass. research director), Faculty of Health, Care and Nursing, NTNU Gjøvik and The Research Centre for Old Age Psychiatry (AFS), SI.

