The second secondary aim of our study is to “*Validate the Edmonton Frail Scale (EFS) as a screening instrument to identify frail patients and patients at risk of adverse events*” (see page 8).

The plan for the analyses was: “*The sensitivity and specificity of EFS in identifying frail patients will be tested against the full GA. EFS’ ability to predict adverse events on the defined outcomes will be assessed with uni- and multivariable regression analyses, controlled for relevant co-variates (e.g. type of cancer, stage of disease, and radiotherapy regimen*” (see page 17)

Partly based on the considerations stated under point 1, we have now decided to perform the validation by investigating the association between the instrument’s scores and OS in addition to association with GA findings. Another strong argument for this is that other well-known and widely used frailty screening instruments, e.g. the G8, have been widely tested against patients’ survival.¹⁻⁵ Thus, for comparison, which is important, we will do likewise.

Before embarking on these analyses, a detailed plan has also been prepared (**Appendix 2**).

3. We have decided not to use the term “frailty” when classifying the patients according to GA. Hence, we will not define the patients as frail or non-frail, but instead classify them according to their number of identified GA impairments.

Our primary hypothesis (page 8) has been revised accordingly, now reading: “*Our hypothesis is that increasing number of GA impairments is associated with increased risk of adverse events as defined, regardless of cancer type, stage, and radiotherapy procedure (localisation, dose, field size)*

This hypothesis and the primary aim of our study will be addressed in paper 3, for which a detailed plan for the analyses has also been prepared (**Appendix 3**)

This amendment also affects paper 2 as the sensitivity and specificity of Edmonton Frail Scale will be evaluated against number of geriatric deficits, not against a classification of frail vs. non-frail patients.

Explanation:

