The overall feasibility of GA performed in the municipality, after EBRT, in this patient cohort will be evaluated in a subsequent paper.

5. We have decided not to assess the patients' muscle mass from available CT scans (as stated in the protocol page 17), hence these scans have not been retrieved.

The reason for this is our experience from a former study⁸ in another cohort of older patients with cancer. From that study, it was clear that as long as a baseline CT scan is not an obligatory part of the study design, or the procedures for such scans are not clearly defined, a large number of patients will not have scans taken within a reasonable time frame or at the appropriate body level including the overall body circumference. Hence, it is highly likely that the number of patients having non-available CT scans would be just as high in the present cohort as in our former study. Hence, the sample size for the planned analyses would most likely be too small. Furthermore, our former study, as well as another one recently

published,⁹ have found no association between muscle mass and frailty as defined by GA. Further investigations on the issue therefore seems futile.

References

5. van Walree IC, Scheepers E, van Huis-Tanja L, et al: A systematic review on the association of the G8 with geriatric assessment, prognosis and course of treatment in older patients with cancer. *J Geriatr Oncol*, 2019

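### The Glasgow Prognostic Score rule leaves some patients without a score (CRP below 10 with albumin at or below 35, or CRP exactly 10) and should be completed, or the analysis formally dropped

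*Combined protocol and SAP*

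**What the plan says.** The rule is in the protocol, section Strategy for the analyses, paragraph on muscle mass and inflammation markers. The GPS combines CRP and serum albumin and "is scored on a scale from 0 to 2". Starting with score 0, the three levels are "CRP < 10 + s-alb > 35, 1 = CRP > 10, any s-alb value, 2 = CRP > 10 + s-alb < 35".

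The same paragraph gives its use: "The association between frailty defined by GA, GPS and muscle mass will be assessed using descriptive statistics and correlation analyses". A further sentence plans regression analyses for survival. Both laboratory values are registered at baseline from routine samples taken within two weeks before radiotherapy (Medical data, Baseline).

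Amendment 4 changes two elements of this paragraph. Under item 3, "we will not define the patients as frail or non-frail, but instead classify them according to their number of identified GA impairments". Item 5 gives up measuring "muscle mass from available CT scans (as stated in the protocol page 17"). Neither item mentions GPS. Appendices 1 to 3, the analysis plans for the first three papers, do not mention it either.

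**The concern.** A score with three levels should give each patient exactly one value. This rule does not. Some combinations of CRP and albumin satisfy no level, and one combination satisfies two.

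The gap matters more than the overlap. An analyst who meets a patient with low CRP and low albumin has to choose score 0, score 1 or exclusion, and nothing in the plan guides that choice. If it is made after the survival data have been seen, it is a post-hoc derivation of a prognostic marker. Patients with low albumin are plausibly not a random subset with respect to nutrition and geriatric impairments. The choice could therefore shift both the association of GPS with the geriatric assessment and the survival contrast between GPS levels.

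**Working it through.** The plan gives no figure for GPS to reproduce. The check has two parts: the logic of the rule, which is certain, and an illustration of size, which rests on assumptions.

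**1. Logic.** Each rule was applied literally to every combination of CRP (below, at, above 10) and albumin (below, at, above 35).

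| | s-alb < 35 | s-alb = 35 | s-alb > 35 |
|---|---|---|---|
| CRP < 10 | none | none | 0 |
| CRP = 10 | none | none | none |
| CRP > 10 | 1 and 2 | 1 | 1 |

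Three of the nine cells receive exactly one score, one receives two, and five receive none.

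If the highest applicable score is taken, the cell with CRP > 10 and s-alb < 35 becomes 2 and the overlap disappears. The five empty cells stay empty, so a precedence rule alone does not complete the score. No other section of the documents supplies an assignment for these cells or says on which side of a limit an equal value falls.

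**2. Size.** The documents report no distribution of CRP or albumin. These inputs are therefore assumptions:

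- albumin: normal, mean 36 to 40 g/L, SD 4 to 5, rounded to integers
- CRP: log-normal, median 6 to 12 mg/L, SD of the log 1.3 to 1.4, rounded to integers
- correlation between albumin and log CRP: -0.4 to -0.6

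The unscored share is P(CRP < 10 and s-alb ≤ 35) + P(CRP = 10). It was obtained by simulation at the ends of these ranges.

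- Lowest share: albumin mean 40, SD 4; CRP median 12, log-SD 1.4; correlation -0.6. About 4% are unscored, of which CRP < 10 with s-alb < 35 makes up about 0.5 percentage points.
- Highest share: albumin mean 36, SD 5; CRP median 6, log-SD 1.3; correlation -0.4. About 26% are unscored, of which CRP < 10 with s-alb < 35 makes up about 18 percentage points.

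For the 301 included patients (Appendix 1), 0.04 × 301 ≈ 12 and 0.26 × 301 ≈ 78.

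The share with CRP exactly 10 depends on reporting precision, which the documents do not state. It is about 3% with integer values and about 0.3% with one decimal. At the low end of the range, most of the unscored share therefore comes from ties, which equality signs alone would resolve.

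About 5% to 30% fall in the overlapping cell under the same assumptions. They are not added to the problem, because reading the rule as highest score wins gives them a score of 2.

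**The case against.** The strongest case on the other side is that little depends on GPS. It is in no stated aim, hypothesis, primary outcome or secondary outcome. The protocol plans it together with muscle mass and frailty, and Amendment 4 has removed muscle mass and replaced the frailty classification. Appendix 1 lists the predictors and adjusters of its survival model without GPS. Paper 4 is about the MoCA test, and a later paper is to cover the feasibility of the geriatric assessment. This stands, and it limits the weight of the point. It does not withdraw the analysis. Item 5 gives reasons that concern CT scans and muscle mass only, and the protocol's background section argues for studying GPS and frailty in its own right.

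A reader might infer four stronger things that the documents do not support.

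- *That the marker cannot be derived.* The raw CRP and albumin values are registered. What is missing is a convention for some combinations, not data.
- *That the overlap collapses the scale to two levels.* Score 2 can exist only if it overrides score 1, so a stated range of 0 to 2 already implies that reading. The overlap is a fault of wording.
- *That GPS has lost its comparator.* Item 3 of Amendment 4 is worded generally and replaces the frail/non-frail classification by the number of impairments. What remains is an unedited paragraph.
- *That low CRP with low albumin should clearly score 0.* The written rule requires albumin above 35 for score 0, and the documents do not say which score the missing combination should get.

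**Conclusion.** The rule is incomplete as written. This follows from the text alone and needs no assumption. Low CRP with albumin at or below 35, and CRP exactly at 10, have no score under any reading. The overlap between scores 1 and 2 is resolved by letting the higher score override, but the plan should say so.

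The number of patients affected is not known. The range of about 4% to 26% (12 to 78 of 301) is an illustration that depends entirely on the assumed laboratory distributions and on integer reporting. The consequence is confined to an ancillary marker that no current analysis plan contains. No primary or secondary outcome is touched. The point is worth correcting because the rule is faulty, the analysis has not been withdrawn, and the repair is cheap.

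**What to change.** Before any GPS analysis, restate the score so that each patient has exactly one value:

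- Score 2: CRP above the limit and s-alb < 35.
- Score 1: CRP above the limit and s-alb ≥ 35.
- State on which side of the limit a CRP of exactly 10 falls.
- For CRP not above the limit, state the score for each albumin level, including s-alb of exactly 35. Fix the score for low CRP with low albumin in advance, after checking the reference that the protocol cites for GPS.
- Run one sensitivity analysis with the alternative assignment of that group (0 versus 1).

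If the GPS analysis is no longer intended, state that it is dropped.

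As a consequential edit, bring the paragraph into line with Amendment 4: use number of GA impairments as the comparator and remove muscle mass.

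The cost is a few sentences of wording and one extra sensitivity table. No new data are needed, since CRP and albumin are already registered at baseline.
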